1.6. Rationale for Current Study

HR+/HER2- breast cancer represents 70% of all breast cancer but remains underrepresented in clinical trials. Although patients with metastatic HR+/HER2- breast cancer typically initially respond to anti-estrogen therapy and CDK4/6 inhibition, inevitably they at some point become resistant and their disease progresses. Generally, patients are then treated with toxic, often intravenous therapies that require frequent clinic and infusion center visits and carry serious potential side effects. An approach to the treatment of metastatic HR+/HER2- negative breast cancer that limits side effects and provides more freedom to patients beyond second or third-line therapies is urgently needed.

SM-88 is transported into cancer cells via the LAT1 transporter, which is upregulated in malignant vs normal tissue and in late-stage compared to early-stage breast cancer, making it an exciting potential targeted oral treatment for breast cancer. Data from the FIH study and compassionate use program of SM-88 indicate that this investigational therapy may be efficacious in the treatment of HR+/HER2- breast cancer and carry a favorable toxicity profile.

We therefore propose a therapeutic approach combining the RP2D of SM-88 used with the conditioning agents MPS in advanced breast cancer to further evaluate the efficacy and safety of this investigational combination.

2. Study Objectives

2.1. Primary Objectives

To determine the objective response rate (ORR) of SM-88 plus the conditioning agents methoxsalen, phenytoin, and sirolimus (MPS) in patients with advanced HR+/HER2 negative breast cancer.

2.2. Secondary Objectives

To assess:

- Progression free survival (PFS),
- Clinical benefit rate (CBR) at ≥ 24 weeks,
- Duration of response (DOR), and
- Safety/tolerability (adverse events, serious adverse events, incidence of dose delays or dose reductions, treatment discontinuations due to adverse events, and all deaths)

2.3. Exploratory Objective

To evaluate changes in cell-free DNA (cfDNA) at baseline (pre-treatment on C1D1), during treatment, and at disease progression.

2.4. Indication

Patients with advanced breast cancer. This pilot trial will enroll a pre-defined number of patients with HR+/HER2- advanced/metastatic breast cancer.

3. Patient Population

3.1. Patient Population, Number of Patients, and Feasibility

3.1.1. Patient Population

This trial will enroll up to 50 evaluable patients with advanced HR+/HER2- breast cancer. Patients will have measurable disease by RECIST v1.1 criteria. This may include at least one lytic bone lesion or mixed lytic - blastic lesion with an associated soft tissue component $\geq 10\text{mm}$ noted on CT or MRI. Patients will also have an adequate PS, hematologic, hepatic, and renal function.

3.1.2. Number of Patients

Fifty evaluable patients will be enrolled.

3.1.3. Feasibility

At the multiple centers participating in this study, we anticipate being able to enroll ~ 29 patients per year. The expected accrual duration will be approximately 24 months.

3.2. Inclusion Criteria

Patients must meet all the following inclusion criteria to be eligible for enrollment in the study:

1. Histologically or cytologically proven diagnosis of breast cancer with evidence of metastatic or locally advanced disease, not amenable to resection or radiation therapy with curative intent.
2. Documentation of ER-positive and/or PR-positive tumor ($\geq 1\%$ positive stained cells) based on most recent tumor biopsy (discuss with the Principle Investigator if results in different biopsies are discordant in terms of hormone receptor positivity) utilizing an assay consistent with local standards.
3. Documented HER2-negative tumor based on local testing on most recent tumor biopsy: HER2-negative tumor is determined as immunohistochemistry score 0/1+ or negative by in situ hybridization (FISH/CISH/SISH) defined by current ASCO/CAP (American Society of Clinical Oncology/College of American Pathologists) guidelines. Patients with equivocal HER2 in situ hybridization results according to current ASCO/CAP guidelines are eligible, as long as they have not received and are not scheduled to receive anti-HER2 treatment.
4. Must have progressed on (or been intolerant of) at least 2 lines of endocrine therapy in either the adjuvant or metastatic setting and progressed on (or been intolerant of) a CDK4/6 inhibitor.
5. Must have received no more than 4 lines of systemic therapy (for example, including but not limited to endocrine therapy, targeted therapy, biologic therapy, chemotherapy, or experimental therapy) for the treatment of breast cancer in the metastatic setting.
6. Premenopausal or postmenopausal female or male patients 18 years of age or older.
7. Measurable disease as defined by RECIST v1.1 criteria (tumor $\geq 1\text{ cm}$ in longest diameter on axial image on computed tomography (CT) or magnetic resonance imaging (MRI) or tumor $\geq 10\text{ mm}$ by caliper measurement on clinical exam and/or lymph node(s) $\geq 1.5\text{ cm}$ in short axis on CT or MRI) at baseline. Lytic bone lesions or mixed lytic-blastic lesions with an associated soft tissue component $\geq 10\text{mm}$ noted on CT or MRI are also included as per RECIST 1.1 criteria. Index lesions must not have undergone prior radiation therapy.
8. Asymptomatic brain metastases are allowed if the lesions are not considered to need local therapy. Previously treated brain metastases are allowed as long as they are > 4 weeks from local therapy, clinically asymptomatic, and not requiring high-dose corticosteroids. Patients may remain on steroids for CNS disease if they are taking a stable dose that is less than 10mg of prednisone per day, or the equivalent.

9. Must be capable of understanding and complying with parameters as outlined in the protocol and able to sign and date the informed consent, approved by the IRB, prior to the initiation of any screening or study-specific procedures.
10. Life expectancy of more than 3 months.
11. ECOG performance status 0-1 (Appendix A, Table 7).
12. Pregnancy must be ruled out in women of childbearing potential. Serum or urine pregnancy test must be negative within 14 days of treatment start in women of childbearing potential and must be willing to have pregnancy test approximately every 4 weeks. Pregnancy testing does not need to be pursued in patients who are judged to be postmenopausal before enrollment, or who have undergone bilateral oophorectomy, total hysterectomy, or bilateral tubal ligation.
 - a. Patients may be considered postmenopausal in the case that one of the following criteria applies:
 - i. Prior bilateral oophorectomy, OR
 - ii. Age \geq 60 years, OR
 - iii. Age $<$ 60 years with intact uterus and amenorrheic for \geq 12 consecutive months **prior to** chemotherapy and/or endocrine therapy exposure
13. Willingness to utilize adequate contraception if of childbearing potential. Women of childbearing potential must use adequate contraception for the duration of protocol treatment and for at least 6 months after the last treatment with SM-88 used with MPS.
 - a. Adequate contraception is defined as one highly effective form (i.e., abstinence, (fe)male sterilization) OR two effective forms (IUD [non-hormonal preferred], condom with spermicidal foam / gel / film / cream / suppository, occlusive cap with spermicidal foam / gel / film / cream / suppository).
14. Must be able and willing to swallow pills whole and retain oral medication.
15. Adequate hematologic parameters (Patients must be able to meet the following criteria without transfusion or receipt of colony stimulating factors within 2 weeks before obtaining sample):
 - a. Absolute neutrophil count (ANC) \geq 1,500/mm³; Patients must be able to meet the criteria without receipt of colony stimulating factors within 2 weeks before obtaining sample
 - b. Platelets \geq 100,000/mm³; Patients must be able to meet the criteria without receipt of transfusion within 2 weeks before obtaining sample
 - c. Hemoglobin \geq 9 g/dL; Patients must be able to meet the criteria without receipt of transfusion within 2 weeks before obtaining sample
16. Serum creatinine clearance \geq 55 mL/min based on Cockcroft-Gault equation
17. Adequate hepatic parameters:
 - a. Aspartate aminotransferase (AST) and/or Alanine aminotransferase (ALT) \leq 3 x ULN
 - b. Total serum bilirubin \leq 1.5 x ULN, except for patients with a documented history of Gilbert's Syndrome who can be enrolled at PI discretion
 - c. For patients with liver metastases, AST and ALT \leq 5x the institution's ULN and/or total bilirubin \leq 3.0x the institution's ULN are acceptable as long as there is no persistent nausea, vomiting, right upper quadrant pain or tenderness, fever, or rash.
18. Alkaline phosphatase \leq 2.5 x ULN (\leq 5.0 x ULN if bone metastases present)
19. Resolution of all acute toxic effects of prior therapy, including radiotherapy to grade \leq 1 or patient's baseline (except toxicities not considered a safety risk for the patient) and recovery from surgical procedures.
20. Must have discontinued all previous therapies for cancer (including endocrine therapy, CDK4/6 inhibitor therapy, cytotoxic chemotherapy, targeted therapy [including, but not limited to, everolimus], radiotherapy, immunotherapy, and investigational therapy) for at least 14 days prior to receiving study drugs.

3.3. Exclusion Criteria

1. Concurrent therapy with other approved or investigational cancer treatment agents, except bisphosphonates, RANKL inhibitors, GnRH agonists such as leuprolide or goserelin.
2. Inability to comply with study requirements.

3. Diagnosis of other invasive cancer except for adequately treated cervix cancer, or more than 5 years since other diagnosis of invasive cancer (including invasive squamous cell cancers due to contraindication for methoxsalen use) without current evidence of disease.
4. Pregnant women or women of childbearing potential without a negative pregnancy test (serum or urine) within 14 days prior to starting study treatment.
5. Breastfeeding must be discontinued prior to study entry.
6. Impairment of gastrointestinal (GI) function or GI disease that may significantly alter the absorption of the study drugs (e.g., ulcerative diseases, uncontrolled nausea/vomiting, chronic diarrhea, malabsorption syndrome, intestinal obstruction, or small bowel resection) at discretion of investigator.
7. Patients with clinically significant liver disease, including active viral (including hepatitis B, hepatitis C, etc) or other known active hepatitis, current alcohol abuse, or cirrhosis.
8. Known chronic hepatitis B virus infection (testing not required prior to enrollment).
 - a. Patients with chronic hepatitis C virus infection may be enrolled if there is no clinical/laboratory evidence of cirrhosis per investigator AND the patient's liver function tests fall within the parameters set in the inclusion criteria, Section 3.2.
9. Uncontrolled HIV infection defined as any of the following 3 criteria: CD4 counts \leq 350 cells/ μ L; serum HIV viral load \geq 400 copies/mL; on a antiretroviral regimen for $<$ 4 weeks prior to treatment with study drugs if anti-retroviral therapy is deemed necessary or appropriate by the investigator.
10. Previous enrollment in this study or any other study investigating SM-88.
11. History of any known drug allergies to any study medication.
12. Clinically significant and uncontrolled major medical condition(s) including, but not limited to uncontrolled nausea/vomiting/diarrhea; active, uncontrolled infection; symptomatic congestive heart failure (New York Heart Association [NYHA] class \geq II); unstable angina pectoris; cardiac arrhythmia requiring hospitalization in the past 3 months; stroke or MI in the past 6 months.
13. Psychiatric illness or social situation that would limit compliance with study requirements.
14. Active uncontrolled or symptomatic brain metastases. Previously treated and clinically stable brain metastases, as per Investigator's judgement, are permitted.
15. Patients with a seizure disorder that is not well controlled or who have required a change in seizure medications within 60 days of enrollment to the trial.
16. Patients with a history of hypersensitivity to phenytoin, its inactive ingredients, or other hydantoins; or a history of prior acute hepatotoxicity attributable to phenytoin.
17. Patients treated, or anticipated to be treated, with delavirdine (due to potential for loss of virologic response and possible resistance to delavirdine or to the class of non-nucleoside reverse transcriptase inhibitors caused by phenytoin).
18. Patients exhibiting idiosyncratic reactions to psoralen compounds.
19. Patients with a history of the light sensitive diseases for which methoxsalen would be contraindicated. Diseases associated with photosensitivity include lupus erythematosus, porphyria cutanea tarda, erythropoietic protoporphyrina, variegate porphyria, xeroderma pigmentosum, and albinism.
20. Patients with cutaneous melanoma or invasive squamous cell carcinomas or a history thereof, except for those with stage 1A melanoma or in complete remission for \geq 5 years (due to contraindication for use of methoxsalen).
21. Patients with a hypersensitivity to sirolimus. Sirolimus does cause immune suppression at the prescribed doses and physicians should note the drugs black box warning to exclude any patient they believe the other exclusion criteria does not reflect.
22. Patients with prior allogenic bone marrow transplant or solid organ transplant organ transplant or being treated, or anticipated to be treated, with cyclosporine (because long-term administration of the combination of cyclosporine and sirolimus is associated with deterioration of renal function).
23. Patients treated, or anticipated to be treated, with a calcineurin inhibitor (because concomitant use of sirolimus and a calcineurin inhibitor increases the risk of calcineurin inhibitor-induced hemolytic uremic syndrome/thrombotic thrombocytopenic purpura/thrombotic microangiopathy [HUS/TTP/TMA]).
24. Current use of known strong inhibitors or inducers of CYP3A4, CYP2C9 or CYP2C19 within 14 days of initiation of study drug. When possible these medications and grapefruit juice should be avoided for the duration of the study treatment and alternate therapies are preferred. For a list, refer to Section 3.5 or Appendix D of the protocol.

3.4. Additional Study Restrictions

3.4.1. Granulocyte Colony-Stimulating Factor (GCSF)

GCSF administration should not be given within 2 weeks of study drug initiation or during the study treatment.

3.4.2. Other Anticancer Therapy

For purposes of this protocol, anti-tumor treatment may be defined as, but is not limited to, anti-cancer agents (anti-estrogen endocrine therapy, cytotoxic chemotherapy, immunotherapy, or biologic therapy), radiotherapy, and investigational agents. An investigational agent is any drug or therapy not currently approved for use in humans. No other anticancer therapy is permitted during the course of the study treatment for any patient (the patient can receive a stable dose of corticosteroids during the study as long as these were started at least 4 weeks prior to enrollment and the total daily dose does not exceed 10mg of prednisone, or the equivalent, per exclusion criteria above). If the patient discontinues study treatment, this restriction no longer applies; however, the patient will remain enrolled in the study for the purpose of collecting subsequent outcomes.

3.4.3. Birth Control

Birth control should be used from the signing of the patient consent form and for 3 months following the last dose of SM-88 and/or MPS. Acceptable methods of birth control include:

- Age \geq 60 years
- At least one highly effective form of contraception (i.e., abstinence, (fe)male sterilization/tubal ligation)
- At least two effective forms (IUD [non-hormonal preferred], condom with spermicidal foam / gel / film / cream / suppository, occlusive cap with spermicidal foam / gel / film / cream / suppository).
- Permanent sterilization, defined as hysterectomy, bilateral salpingectomy, bilateral oophorectomy, or bilateral orchidectomy
- Postmenopausal, defined as a female patient $<$ 60 years of age with intact uterus and amenorrhoeic for \geq 12 consecutive months **prior to** chemotherapy and/or endocrine therapy exposure

In addition, men must not conceive a child or donate sperm during SM-88 and/or MPS therapy, and for 6 months after receiving the last dose of study therapy.

3.4.4. Breastfeeding

Patients must not breast-feed from the first dose of SM-88 and/or and for 1 month following the final dose of SM-88 and/or MPS.

3.4.5. Blood Donation

Patients must not donate blood during the study or for 90 days after the last dose of study treatment.

3.5. Other Prior and Concomitant Therapy

Patients will be instructed to consult the Investigator or other appropriate study personnel before taking any new medications, supplements, or vaccines during the study.

Concomitant medications taken within 30 days prior to baseline will be recorded. At each study visit, all concomitant medications taken since the previous visit, including prescription and non-prescription medications, vitamin and mineral supplements, herbal and naturopathic remedies, vaccines, and supportive therapies, will be recorded.

- Treatment with any other anticancer agents is not allowed except for bisphosphonates, RANK-L inhibitors, and GnRH agonists
- Medications that are clinically known to induce or inhibit metabolic enzymes or transporters, including CYP3A4, CYP2C9, CYP2C19, and p-glycoprotein (Pgp) must be used with caution or

avoided. Known strong inhibitors or inducers of CYP3A4, CYP2C9 or CYP2C19, such as those listed below, are not allowed within 14 days prior to the first dose of study medication and for the duration of study treatment. When possible these medications and grapefruit juice should be avoided for the duration of the study treatment and alternate therapies are preferred:

- CYP2C9:
 - Strong inhibitors: fluconazole
 - Strong inducers: none known
- CYP2C19:
 - Strong inhibitors: fluconazole, fluvoxamine, ticlopidine
 - Strong inducers: none known
- CYP3A4:
 - Strong inhibitors: atazanavir, boceprevir, ciclosporin, clarithromycin, conivaptan, danazol, erythromycin, gemfibrozil, grapefruit juice, indinavir, itraconazole, ketoconazole, lopinavir/ritonavir, mibefradil, nefazodone, nelfinavir, osaconazole, ritonavir, saquinavir, telaprevir, telithromycin, voriconazole,
 - Strong inducers: avasimibe, carbamazepine, phenobarbital, rifabutin, rifampin, St. John's Wort
 - Delavirdine
 - Cyclosporine
 - Calcineurin inhibitors

3.5.1. Prior Surgery

Patients must have fully recovered from all effects of surgery.

3.5.2. Supportive Care

Patients should receive best supportive care and treatment of symptoms during the study as appropriate, including transfusion of blood and blood products, oxygen therapy, nutritional support, intravenous fluids, and treatment with appropriate medications (antibiotics, antiemetics, antidiarrheals, and analgesics, etc.). Medications that are given for supportive care, such as appetite stimulation, may be given concurrently.

3.5.2.1. Bisphosphonates and denosumab

Bisphosphonates and denosumab are permitted for the treatment of osteoporosis and prevention of skeletal related events for patients with bone metastases.

3.5.2.2. GnRH agonists

GnRH agonists are permitted at the discretion of the treating physician.

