3.6.2. Evaluable Patients

3.6.2.1. Objective Response Evaluable

To be considered evaluable for the primary endpoint of ORR as determined by RECIST v1.1, the patient must meet all inclusion/exclusion criteria and remain on study treatment at least until the first re-staging after cycle 2 of SM-88 used with MPS unless they are taken off for disease progression, clinical progression, or death related to the underlying solid tumor malignancy (as determined by the treating oncologist) in which case they **will be** deemed evaluable. However, patients who have initiated therapy and who withdraw from the study for any reason other than clinical or radiographic progression, or death believed unrelated to their underlying solid tumor malignancy **will not be** considered evaluable for response. Reasons for patients who have initiated therapy, but are no longer evaluable for response could include (but are not limited to):

- The patient cannot tolerate therapy despite dose modifications, and there is no evidence of clinical/radiographic disease progression at the time of stopping therapy
- An unexpected and/or unrelated medical illness, such as a stroke or myocardial infarction that is considered unrelated to the underlying solid tumor malignancy
- An unexpected trauma or death that is considered unrelated to the underlying solid tumor malignancy

If a patient is deemed to be non-evaluable for the primary endpoint of ORR they will be replaced.

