11.0 APPENDICES

APPENDIX A: STUDY ELIGIBILITY CHECKLIST

A Phase II trial of SM-88 in patients with metastatic hormone receptor-positive and HER2-negative (HR+/HER2-) breast cancer

Study ID: _____

Instructions: This form should be completed by the research staff before registering the patient into the trial.

Completed form can be emailed to Georgetown Project managers [REDACTED]

- MedStar Georgetown University Hospital
- MedStar Washington Hospital Center
- MedStar Franklin Square Medical Center
- MedStar Good Samaritan Hospital
- Hackensack University Medical Center

INCLUSION CRITERIA (ALL ITEMS MUST BE CHECKED YES)

YES NO	
 	Histologically or cytologically proven diagnosis of breast cancer with evidence of metastatic or locally advanced disease, not amenable to resection or radiation therapy with curative intent.
 	Documentation of ER-positive and/or PR-positive tumor ($\geq 1\%$ positive stained cells) based on most recent tumor biopsy (discuss with the Principle Investigator if results in different biopsies are discordant in terms of hormone receptor positivity) utilizing an assay consistent with local standards.
 	Documented HER2-negative tumor based on local testing on most recent tumor biopsy: HER2-negative tumor is determined as immunohistochemistry score 0/1+ or negative by in situ hybridization (FISH/CISH/SISH) defined by current ASCO/CAP (American Society of Clinical Oncology/College of American Pathologists) guidelines. Patients with equivocal HER2 in situ hybridization results according to current ASCO/CAP guidelines are eligible, as long as they have not received and are not scheduled to receive anti-HER2 treatment.
 	Must have progressed on (or been intolerant of) at least 2 lines of endocrine therapy in either the adjuvant or metastatic setting and progressed on (or been intolerant of) a CDK4/6 inhibitor.
 	Must have received no more than 4 lines of systemic therapy (for example, including but not limited to endocrine therapy, targeted therapy, biologic therapy, chemotherapy, or experimental therapy) for the treatment of breast cancer in the metastatic setting.
 	Life expectancy of more than 3 months.

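### GnRH agonists are permitted with no start-date condition, while the 14-day washout criterion and its Appendix A line do not exempt them (minor; cheap improvement)

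*Combined protocol and SAP*

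**What the plan says.** **Where the agonists are allowed.** Section 3.5.2.2: "GnRH agonists are permitted at the discretion of the treating physician". Section 3.3 item 1 excludes "Concurrent therapy with other approved or investigational cancer treatment agents, except bisphosphonates, RANKL inhibitors, GnRH agonists such as leuprolide or goserelin". Section 3.5 repeats the allowance: "Treatment with any other anticancer agents is not allowed except for bisphosphonates, RANK-L inhibitors, and GnRH agonists". The exclusion part of the Appendix A checklist carries the same exception as Section 3.3 item 1. None of the four places sets a start date, a stable-use period or a menopausal condition.

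**Where they are not exempted.** Section 3.2 item 20 reads "Must have discontinued all previous therapies for cancer (including endocrine therapy, CDK4/6 inhibitor therapy, cytotoxic chemotherapy", continues through further treatment classes, and requires at least 14 days off them before study drug. The corresponding Appendix A inclusion line has the same content, under the instruction "INCLUSION CRITERIA (ALL ITEMS MUST BE CHECKED YES". Section 3.4.2 states that "No other anticancer therapy is permitted during the course of the study treatment for any patient". The only exception given there is a "stable dose of corticosteroids during the study as long as these were started at least 4 weeks prior to enrollment", with a dose limit.

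**How this reaches the primary endpoint.** Section 3.6.2.1 makes evaluability for ORR depend on eligibility: "the patient must meet all inclusion/exclusion criteria and remain on study treatment at least until the first re-staging after cycle 2", apart from patients taken off early for progression or disease-related death. Non-evaluable patients are replaced. Section 7.5 takes best response from treatment start to progression. Section 8.4.1 computes ORR in all patients with at least one cycle. Neither addresses an agonist started after baseline.

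**The concern.** There are two separate problems.

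The first is eligibility. Take a premenopausal patient, or a man, on continuing goserelin. The exclusion line of the checklist lets the patient in. Read literally, the inclusion line asks for the agonist to have been stopped for 14 days. Both lines are on the same signed form. A literal reader could stop ongoing suppression and restart it, or could later question the patient's eligibility and hence evaluability for ORR.

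The second is attribution. The trial has one arm, the disease is hormone receptor-positive, and Section 3.2 item 6 admits premenopausal women and men. If an agonist is started or restarted after the baseline scan, a later response cannot be separated from a response to SM-88 plus MPS, yet it would count toward both cut-offs. Corticosteroids have a start-date rule in Section 3.4.2; GnRH agonists, which are hormonally active in this disease, have none.

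**Working it through.** **Text comparison**

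| Place | GnRH agonists exempt? | Start-date condition? |
|---|---|---|
| 3.3 item 1 | Yes | No |
| 3.5 | Yes | No |
| 3.5.2.2 | Yes | No |
| Appendix A, exclusion line | Yes | No |
| 3.2 item 20 | No | 14-day washout for all prior therapy |
| Appendix A, inclusion line | No | Same as 3.2 item 20 |
| 3.4.2 | No (general ban) | Only for corticosteroids |

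Four places permit the agonists by name and none bans them by name. The contradiction therefore comes from a missing exemption. The checklist is inconsistent between two of its lines; it is not silent on the agonists.

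**The plan's own design figures (Section 8.3).** Inputs: n1 = 30, continue at 3 or more responses; 20 further patients, success at 8 or more of 50; null 0.095, alternative 0.20. The probability of declaring the treatment promising at true rate p is

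R(p) = sum over x ≥ 3 of P(Bin(30, p) = x) × P(Bin(20, p) ≥ 8 − x).

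- R(0.095) = 0.0955, against a stated limit of 0.1.
- R(0.20) = 0.8022, against a stated 0.8.

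The design reproduces.

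**Illustration of the upward effect.** Let s be the share of patients who newly start an agonist on study and q the share of those who respond because of it. The documents give neither, so both are assumptions. With an otherwise inactive regimen, only patients who would not have responded (1 − 0.095 = 0.905) can add responses:

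observed rate = 0.095 + 0.905 × s × q; extra responses per 50 = 50 × 0.905 × s × q.

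| s | q | Observed rate | R | Extra responses per 50 |
|---|---|---|---|---|
| 0 | – | 0.0950 | 0.0955 | 0 |
| 2% | 5% | 0.0959 | 0.0996 | 0.045 |
| 2% | 10% | 0.0968 | 0.1038 | 0.091 |

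The stated 0.1 limit is reached at a true rate of about 0.0960, so even a small excess uses up the margin. The resulting change in error probability is still less than one percentage point (0.1038 − 0.0955 = 0.0083).

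**The case against.** The case for leaving the text alone is substantial.

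- *Intent is clear.* The version 1.5 entry in the amendment log records that the allowance was clarified in the exclusion criteria and Sections 3.5 and 3.5.2.2, and the current text matches it. Item 20 can be read as a general washout, with Section 3.3 item 1 naming what may continue. This stands, and it makes the permissive reading almost certain.
- *Section 3.4.2 is a general statement.* It does not exempt bisphosphonates or RANKL inhibitors either, although Sections 3.3 and 3.5 permit both. This stands, so 3.4.2 is weak evidence of a conflict.
- *Sites do not decide alone.* Section 3.7.2 requires central review of records before treatment starts, and monthly calls take site questions (Section 3.7.4). A reader might infer that sites will freely continue, restart or exclude such patients. The documents do not support that. They do, however, give the central reviewers no written rule for item 20.
- *New starts are an inference.* Section 3.5.2.2 sits under supportive care, and Section 4.3.12 withdraws patients who need alternate antineoplastic agents. No sentence says that an agonist may be newly started. But an unconditional permission by name does not prevent it, and Section 4.3.12 does not mention the agonists.
- *The population is endocrine-pretreated.* Section 3.2 item 4 requires progression on, or intolerance of, at least two endocrine lines and a CDK4/6 inhibitor. This makes a response to a newly added agonist unlikely. It does not exclude one, because intolerance qualifies and the endocrine lines may have been adjuvant.

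**Conclusion.** The point holds as a minor defect with a cheap remedy. As written, Section 3.2 item 20 and its Appendix A line contradict an otherwise consistent permission. That permission has no timing limit, so a response after an agonist newly started on study would count in the primary ORR.

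The upward bias is probably small and cannot be derived from the documents. The shift in type I error from 0.0955 to about 0.100-0.104 rests wholly on the assumed 2% start rate and 5-10% response rate. Larger shifts need start and response rates for which the documents give no basis. The eligibility contradiction could act in either direction and has no estimable size.

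A reader might infer a larger impact from how often one responder decides the trial: it ends at exactly 8/50 with probability 0.052 at a true rate of 9.5%, and passes stage 1 but ends at exactly 7/50 with probability 0.088. These probabilities describe the decision rule. They would apply to any question about a single responder and do not measure the effect of GnRH agonist use.

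**What to change.** 1. In Section 3.2 item 20, Section 3.4.2 and the Appendix A inclusion line, exempt GnRH agonists that were started before the baseline scan and are continued on study.
2. In Section 3.5.2.2, allow continuation of such an agonist and bar a new start during study treatment. State that a delayed dose of an ongoing agonist is not a new start. The sponsor should choose the lead time before the baseline scan. Four weeks, the interval used for corticosteroids in Section 3.4.2, is one option, but nothing in the protocol requires it.
3. Record any new start on study as a protocol deviation, and report ORR with and without those patients as a sensitivity analysis. Section 3.5 already has concomitant medications recorded at every visit. The primary counting rule stays as it is.

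The cost is an amendment, which Section 10.1 requires the IRB to approve before use, one extra table, and possibly a short entry delay for the few patients who newly need suppression. The sample size, cut-offs, and calculated type I error and power (0.0955 and 0.8022) do not change. A lead time reduces the confounding but does not remove it entirely.
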